#### Outcomes

Our primary outcome will be change in hemoglobin and hematocrit in the 3rd trimester. Based on the available evidence with hypothesize that alternate day dosing of oral iron supplementation will be superior or at least not inferior to daily oral iron supplementation. Additionally we aim to assess the secondary outcomes as listed in the introduction obtained by chart review. Data to be collected includes population characteristics including demographics and data points described in the outcomes listed under the introduction obtained by chart review. A detailed explanation of the analysis of the primary outcome is described in a later section.

#### 5. Sub-Study Procedures:

Not applicable

### 6. Criteria for Inclusion of Subjects:

- Maternal age  $\geq$  18 years and <50 years
- Prenatal care provided at UTMB
- Hemoglobin below 11 g/dl in the first trimester and/or 10.5 g/dl in the second trimester
- Microcytic anemia
- Singleton gestation

### 7. Criteria for Exclusion of Subjects:

- Enrolled in another trial that may affect outcome at the discretion of the PI
- Diagnosis of malabsorptive disorder or history of gastric bypass procedure
- Known diagnosis of anemia other than iron deficiency (thalassemia, macrocytic anemia, sickle cell, etc.)
- History of cardiopulmonary disease

• Severe anemia of requiring transfusion or parental iron at time of randomization

### 8. Sources of Research Material:

The primary and secondary outcomes for this trial will be obtained from chart review for enrolled patients.

### 9. Recruitment Methods and Consenting Process:

Patients receiving prenatal care at the UTMB/RMCHP clinics will be screened to identify patients with a hemoglobin below 11 g/dl in the first trimester and/or 10.5 g/dl in the second trimester who also satisfy inclusion and exclusion criteria. RMCHP clinical providers will be educated about the trial prior to enrollment. We plan to identify these patients by screening the charts of patients scheduled in clinic to identify potential subjects. Information to be reviewed as part of the screening process will be hemoglobin laboratory data and relevant exclusion and inclusion history. Research staff will function as the screeners and will alert providers that their patient is a potential subject. The provider caring for that patient will then be informed of the patient's eligibility. Research staff will work with the provider to ensure that the study intervention is appropriate therapy for the patient. If the provider agrees that the study intervention is appropriate, the provider will introduce the research staff to the patient who will then explain the study the patient as part of the consenting process. A screening log will be used to track all subjects approached for the study. At the time of consent and randomization, the patient will be educated as to the dosing regimen as well as the routine treatment surveillance that will occur. This will be done by the research staff consenting the patient.

### Spanish speakers:

Spanish speaking patients will be screened by use of a Spanish interpreter and all patient study materials and surveys will be translated into Spanish.

#### Consenting process:

Written consent will be obtained at the follow up visit by direct person-to-person conversation. The PI or a collaborator will be responsible for the informed consent. Subjects will be given time needed in order to fully understand and read the consent forms. All efforts will be made by the research staff to answer all questions the subject has and to ascertain that subjects have the right to refuse to participate in the study. The consent form and process will describe that patients will be randomly assigned to either the study or control group. Each patient will be informed that participation is completely voluntary and in no way will affect the prenatal care they receive.

### **10. Potential Risks:**

### Randomization Risk:

Since treatment will be randomized, it is possible that one or more of the other treatment groups will have more benefit or lower side effects than the other group.

### Loss of Confidentiality:

Any time information is collected, there is a potential risk for loss of confidentiality. Every effort will be made to keep the subject's information confidential; however, this cannot be guaranteed.

### Persistence of anemia

The every other day dosing group receives iron less frequently than the daily iron dosing group. This could cause an increased risk of persistence of anemia as the every other day dosing may not work as well as every day dosing.

#### 11. Subject Safety and Data Monitoring:

The PI and research coordinator will be responsible for monitoring the safety of this study. Details of monitoring submitted separately.

### 12. Procedures to Maintain Confidentiality:

Data collection will be identified with a participant ID number. Data will be collected and stored with the participant ID code only. The master enrollment log linking subject identifiers with study ID numbers will be kept in a password-protected database. Relevant data variables (specified under outcomes) will be collected by chart review and placed into an Excel or Access file. These files will not contain identifiable information and will be stored in password protected, secured UTMB servers. The research coordinator and PI will be available to monitor the data and correct any discrepancies based on source documents if needed.

## 13. Potential Benefits:

The potential benefits of the study to the intervention group (alternate day dosing) include:

- 1. Improved fractional absorption of iron with corresponding improvement of anemia compared to standard oral iron replacement therapy
- 2. Decreased GI side effects with alternate day dosing

## 14. Biostatistics:

We hypothesize that the intervention group will have a higher hemoglobin level in the third trimester than the standard group. The primary analysis will be conducted on an intention-to- treat basis. Between-group differences in continuous variables, will be assessed using Student t test or Man-Whitney rank sum test and results will be given as mean, standard deviation or median range as appropriate. Categorical variables will be assessed using the Pearson chi-square test or Fisher exact test as appropriate. For dichotomous endpoints, relative risk (RR) and 95% CI values will be calculated. P <0.05 will be considered significant. The analysis will be performed after study completion.

Based on our historical data at our center of 56 anemic women with iron deficient anemia that received standard daily iron supplementation: third trimester hemoglobin mean of  $10.27 \pm 1$  g/dL. We will first do a noninferiority approach. If noninferiority is not met, we will do a superiority analysis. For the noninferiority: If there is truly no difference between the standard and experimental treatment, then 68 subjects will be required to be 90% sure that the lower limit of a one-sided 95% confidence interval (or equivalently a 90% two-sided confidence interval) will be above the non-inferiority limit of -1. For the superiority: We estimate that a minimum sample of 39 per group, total N= 78 women will be needed to provide a power of 90% with a two-sided alpha level of 0.05 and a 1 g/dL difference in hemoglobin between control and intervention. We plan to enroll 86 patients in order to account for up to 10% missing data or loss to follow up. If no differences are noted among groups (non inferiority hypothesis failed) we will be performing a superiority approach. Stata 16 will be used for the statistical analysis.

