#### Primary outcomes:

• Change in hemoglobin and hematocrit in the 3rd trimester

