## 3. Concise Summary of Project:

This trial will be a comparative pragmatic open label randomized controlled trial of daily versus alternate day dosing of oral iron in anemic pregnant patients.

Two randomly assigned groups will be compared during the antepartum period:

- 1. Control Group: standard of care, daily oral iron supplementation (325 mg PO daily ferrous sulfate)
- 2. Intervention Group: alternate day dosing oral iron supplementation (650 mg PO every other day ferrous sulfate)

325mg Ferrous sulfate is a standard oral iron supplement providing 65 mg of elemental iron per dose. Standard dosing recommendations for the treatment of iron deficiency anemia is between 65 to 200 mg elemental iron daily.

Each group will receive a phone survey 2-4 weeks after initiation of therapy to assess side effects of each group as well as compliance. Call is anticipated to last approximately 10-15 minutes. This survey has previously been validated in assessing gastrointestinal symptoms for those taking oral iron supplementation (33).

The number of subjects studied will be 86 subjects at UTMB, we plan to approach and consent up to 96 patients to allow for screening failures, early withdrawals, and patients lost to follow-up, and patients who must withdraw due to failure of therapy. Failure of therapy for the purposes of this study will be patients who require parental iron supplementation or transfusion. Study to last an anticipated length of 3 years. If our sample size is not achieved, we will submit to the IRB an addendum to increase the number of consented subjects to achieve the desired sample size.

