#### Additional details

The routine prenatal visits for pregnant patients with anemia include at least monthly venipunctures to monitor the treatment of anemia and intervene if necessary. Our primary outcome of 3rd trimester hemoglobin as well as laboratory secondary outcomes are convenient data points collected in the standard treatment and surveillance of anemia in pregnancy. As such patients will not need any study specific venipuncture or visits. Prenatal visits are frequent with monthly visits in the 1st trimester, bi-monthly visits in the 2nd trimester, and weekly visits in the 3rd trimester with 24 hour after hours care phone services available. The frequency and ready availability of appointments ensures that any symptomatic patient will quickly be seen and evaluated.

Any subject that requires escalation of treatment beyond oral supplementation (IV iron infusion or blood transfusion) will be referred to receive appropriate intervention. These subjects will still be included in the intent-to-treat analysis. The routine surveillance of anemic pregnant patients described above ensures that any treatment failure will be quickly identified and addressed.

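### The primary outcome is given both as change in hemoglobin and hematocrit and as third-trimester hemoglobin; the plan should fix one hemoglobin outcome, one baseline, one draw rule and one analysis

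*Combined protocol and SAP*

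**What the plan says.** The outcome appears in two forms, both in current text.

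- Change, two variables: the entry under Primary outcomes in section 1 begins "Change in hemoglobin and hematocrit in the" third trimester. The Outcomes paragraph of section 4 repeats it: "Our primary outcome will be change in hemoglobin and hematocrit in the" third trimester. Neither ranks hemoglobin against hematocrit or names the value from which change is measured.
- Level, one variable: Additional details in section 4 says "Our primary outcome of 3rd trimester hemoglobin as well as laboratory secondary outcomes are convenient data points". Section 14 says "We hypothesize that the intervention group will have a higher hemoglobin level in the third trimester than the standard group". The aim in the Introduction is also worded in terms of third-trimester hemoglobin.

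The Outcomes paragraph refers the reader to a later section for the detailed primary analysis. That section is 14. It gives a historical third-trimester hemoglobin of 10.27 ± 1 g/dL, says "We will first do a noninferiority approach", and requires that the lower confidence limit "will be above the non-inferiority limit of -1" (no unit is given; I read g/dL). It never mentions change or hematocrit. For continuous variables in general it says "Between-group differences in continuous variables, will be assessed using Student t test or Man-Whitney rank sum test", with no baseline adjustment.

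On timing, women are screened at the first visit and approached for consent at the next one (section 4, Screening). Brief Study Design and Rationale describes blood draws no less than once a trimester; Additional details describes them no less than once a month.

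**The concern.** An analyst could report the unadjusted difference in third-trimester hemoglobin, or the unadjusted difference in change, and claim to have followed the plan either way. Hematocrit could also be reported as primary, although it has no margin. The baseline is not named, and a woman may have several third-trimester values with no rule for choosing among them.

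The trial is a "comparative pragmatic open label randomized controlled trial" and its outcomes come from chart review (section 8), so these choices could be made with results in view. No selective intent is needed for harm: on the same data the two hemoglobin analyses can fall on opposite sides of −1.

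**Working it through.** **Inputs.** From section 14: 39 per arm, SD 1 g/dL, margin −1, one-sided 5%. Not in the documents, so assumed: baseline SD sb = 0.3–0.6 g/dL (eligibility caps baseline hemoglobin) and baseline to third-trimester correlation r = 0.1–0.5.

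**1. The plan's own sample sizes.** These show which SD to carry forward.

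- Superiority, SD 1, difference 1: n = 2(1.960 + 1.282)² = 21.0, so 22 per arm. The plan has 39. Implied SD = √(39/21.01) = 1.36.
- Non-inferiority, SD 1: n = 2(1.645 + 1.282)² = 17.1, so 18 per arm or 36 in total. The plan has 68, read as a total. Implied SD = √(34/17.13) = 1.41.

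The figures do not reproduce at SD 1, so I use SD = 1, 1.36 and 1.41 below. Why they do not reproduce is a separate question.

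**2. Gap between the two estimates.** Level difference minus change difference equals the baseline difference between arms. Its SE is sb × √(2/39) = sb × 0.2265, which is 0.068 to 0.136. Multiplied by 1.96, the two estimates differ by more than 0.13 to 0.27 g/dL in 1 trial of 20.

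**3. Opposite verdicts.** With level SD s:

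- SD of change: sc = √(s² + sb² − 2·r·s·sb)
- correlation of the two estimates: ρ = (s − r·sb)/sc
- P(non-inferior on one scale) = Φ((d + 1)/SE − 1.645), where d is the true difference
- P(opposite) = pL + pC − 2·pBoth; P(either) = pL + pC − pBoth, with pBoth from the bivariate normal

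One corner in full: s = 1, sb = 0.6, r = 0.1, d = −0.5.

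- sc = √(1 + 0.36 − 0.12) = 1.114; ρ = 0.94/1.114 = 0.844.
- SEs are 0.2265 (level) and 0.2522 (change).
- pL = Φ(0.563) = 0.713; pC = Φ(0.338) = 0.632; pBoth = 0.5855.
- P(opposite) = 0.7133 + 0.6323 − 2 × 0.5855 = 0.1746, about 17%.

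Over the whole assumed range:

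| Quantity | SD 1 | SD 1.36 | SD 1.41 |
|---|---|---|---|
| Opposite verdicts, true −0.5 | 8–17% | 7–16% | 7–16% |
| Opposite verdicts, true −0.25 | 2–7% | 5–12% | 5–12% |
| Opposite verdicts, true 0 | 0.2–0.9% | 1.9–4.5% | 2.2–5.1% |
| Non-inferior on either scale, true −1 | 6.2–7.5% | 5.9–6.8% | 5.8–6.8% |
| Non-inferiority power, level, true 0 | 99.7% | 94.5% | 93.1% |

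**4. Hematocrit.** If either hemoglobin or hematocrit sufficed, false non-inferiority would be 6.8% at an assumed correlation of 0.90 and 6.0% at 0.97. This also assumes an equivalent hematocrit margin, which the plan does not give.

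**5. Baseline as covariate.** If level = a + b·arm + c·baseline, then change = level − baseline = a + b·arm + (c − 1)·baseline. The arm effect b and its SE are the same for level and change.

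**6. Precision.** The variance ratio against the unadjusted level is about (1 − r²)(1 + 1/74). Eligibility truncates baseline hemoglobin. If only the lowest 10, 20 or 30% qualified (assumed), a population correlation of 0.5 would fall to 0.23, 0.26 or 0.28. The ratio is then 0.959, 0.945 or 0.931, a saving of 4–7%. Below r = 0.115 there is a trivial loss: at r = 0.1 the ratio is 1.003. If r within the trial were as high as 0.5, the ratio would be 0.76.

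**The case against.** The strongest reply is that the plan has an operative outcome. The Outcomes paragraph defers to section 14, section 14 is about third-trimester hemoglobin, and the Introduction agrees, so the change wording is merely loose. This has weight, but it does not settle the matter. The formal list of primary outcomes and the Outcomes paragraph both still say change in two variables, and section 14 does not set that aside.

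Four stronger readings are tempting and not supported.

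- That level and change ask different questions. Under randomisation they are two estimators of one arm difference, and −1 applies to both.
- That the rank-sum option leaves non-inferiority untestable. Section 14 already bases that test on a confidence limit, and the sentence on tests covers continuous variables generally. What is missing is the method for the interval.
- That the trial lacks power for non-inferiority. At 39 per arm and zero difference, power for the level is 93–99.7% across the three SDs.
- That the sample sizes show change was intended. SD 1 at both times with zero correlation gives a change SD of 1.41, but that needs 43 per arm for superiority and 70 in total for non-inferiority, not 39 and 68. The documents do not say it was used.

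It is also fair that the effect is modest at the planning assumption of no difference, that inflation above 5% requires picking the better scale, and that an unadjusted t test on one prespecified outcome would be valid. Regression is preferred because it removes the conflict whichever form the sponsor intended.

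**Conclusion.** The point holds as a gap in prespecification, and it should be closed. The textual conflict stands without any calculation. Its size depends on the assumed baseline SD and correlation: opposite non-inferiority verdicts in about 7–17% of trials at a true −0.5 g/dL; at zero difference, under 1% if the SD is 1 and about 2–5% if it is 1.36–1.41. Choosing the more favourable scale would give about 6–7.5% false non-inferiority instead of 5%. A reader might infer that the sponsor means to choose after seeing results. Nothing in the documents shows that; they only leave it possible.

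**What to change.** 1. In Primary outcomes (section 1), Additional details and Outcomes (section 4) and section 14, name third-trimester hemoglobin as the single primary outcome and make hematocrit secondary.
2. In section 14, estimate the arm difference by linear regression on arm and baseline hemoglobin. Use that model's confidence interval for both the −1 g/dL comparison and superiority, and state the margin's unit.
3. Define baseline as the last hemoglobin on or before randomisation. Fix one gestational-age window and one rule for choosing among several draws, applied identically in both arms.
4. Report by arm how many counted values follow IV iron or transfusion. Add a sensitivity analysis using the pre-escalation third-trimester value where one exists.

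A window is better than simply taking the last value before delivery, which would more often follow escalation. Hypothetically, if 10 percentage points more counted values in the worse arm followed escalation and each rose by 0.5–1 g/dL, the arms would move 0.05–0.10 g/dL closer. False non-inferiority would then be Φ(0.05/0.2265 − 1.645) = 7.7% to Φ(0.10/0.2265 − 1.645) = 11.4%, more than the level/change choice costs.

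The change is to wording only, with no new blood draws. Hematocrit loses primary status, and some draws will fall outside the window, so its width should respect section 14's allowance of up to 10% missing data.

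Separately, section 3 provides for withdrawal on failure of therapy, while Additional details keeps such women in the intention-to-treat analysis. Those passages must be reconciled as a point of their own.

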### 2. Background:

The prevalence of iron deficiency anemia (IDA) in reproductive aged women aged 20-49 years is estimated to be 9.2% (7). In pregnancy, rates of anemia affect between 18-21% of pregnant women in the United States with non-Hispanic blacks and teenage mothers affected at even higher rates (8, 9). Outside of pregnancy anemia has been estimated to account for 8.8% of global disability (10). However, during pregnancy IDA has been associated with increased risk of low birth weight, preterm delivery, and perinatal mortality as well as a possible association with postpartum depression and poor mental and psychomotor performance testing of offspring (8). Gabbe et al. notes that "In developing nations, severe anemia is alarmingly common and is a major cause of maternal morbidity and mortality" (11). Pregnant patients with anemia are at further risk for blood transfusion in the event of postpartum hemorrhage.

In pregnancy, hematology physiology changes drastically. Total blood volume increases by approximately 50% and red blood cell mass increases by 25% (8). The relative increase of blood volume compared to red blood cell mass causes a physiologic anemia of pregnancy and therefore the hemoglobin and hematocrit threshold for diagnosing anemia in pregnancy are different than that of a non-pregnant adult (8). This increase in red blood cell mass, combined with the needs of the fetus, placenta, and normal anticipated blood loss from vaginal delivery represent a total additional need of 1,000 mg iron for a pregnancy. It is therefore, unsurprising that the most common etiology of anemia in pregnancy is iron deficiency, representing 75% of all anemia in pregnancy (11).

The World Health Organization (WHO) recommends that pregnant women take 60 mg elemental iron daily while noting that 30 mg might be sufficient (12, 13). The American College of Obstetrics and Gynecology (ACOG) however notes that, "It is unclear whether iron supplementation in well-nourished pregnant women who are not anemic affects perinatal outcomes" (8). Most pregnant women receive some level of iron supplementation through the administration of prenatal vitamins.

The definitive diagnosis of iron deficiency should be made with measurement of serum iron, ferritin, and transferrin saturation; however, recent iron therapy and extended periods of anemia can complicate the interpretation of these results (11). The diagnosis of iron deficiency is often presumed in pregnant patients with

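### The primary hemoglobin comparison is valid but does not adjust for screening hemoglobin or entry trimester, so precision available from eligibility data goes unused

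*Combined protocol and SAP*

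**What the plan says.** **Analysis.** Section 14 (Biostatistics) states that "The primary analysis will be conducted on an intention-to- treat basis" and that "Between-group differences in continuous variables, will be assessed using Student t test or Man-Whitney rank sum test". It names no covariate, regression model or sensitivity analysis. Non-inferiority is read from a lower one-sided 95% confidence limit that "will be above the non-inferiority limit of -1".

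**Outcome.** Two versions appear. Section 4, under Outcomes, has "Our primary outcome will be change in hemoglobin and hematocrit in the 3"rd trimester, as does the list of primary outcomes in section 1; neither names the baseline for the change. Section 14 speaks of the level: "We hypothesize that the intervention group will have a higher hemoglobin level in the third trimester than the standard group". Section 4, under Additional details, also refers to the third-trimester value.

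**What is on file.** Section 6 requires "Hemoglobin below 11 g/dl in the first trimester and/or 10.5 g/dl in the second trimester". Both the value and the trimester must therefore be known before a woman can be enrolled, and section 9 lists hemoglobin results among the data reviewed at screening.

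**Randomization.** Section 4, under Screening, describes a randomization log and states no stratification.

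**The concern.** Screening hemoglobin is a natural predictor of later hemoglobin. Gestation at entry is a plausible second one: the plan uses different cut-offs by trimester, and an earlier entrant has a longer course of treatment before the third-trimester sample. Neither factor enters the design or the model, so the variation they explain stays in the error term.

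The non-inferiority conclusion depends on where one confidence limit falls, and the superiority conclusion on a test with about 39 women per arm. Unexplained variation widens the interval in the first case and lowers power in the second. The data that would reduce it are already collected.

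**Working it through.** **Inputs from section 14.** SD of third-trimester hemoglobin 1 g/dL (56 historical women); limit -1, read as g/dL; one-sided 5% for non-inferiority; two-sided 5% and a 1 g/dL effect for superiority; 90% power; 68 women in total for non-inferiority and 39 per group for superiority.

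**Assumed, because the documents do not give them.** Correlation r of 0.3 to 0.5 between screening and third-trimester hemoglobin; screening SD of either 0.7 or 1 g/dL.

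**Step 1: the plan's own sample sizes.** The plan says "If there is truly no difference between the standard and experimental treatment, then 68 subjects will be required to be 90% sure".
- Non-inferiority, SD 1: n per arm = 2 × (1.645 + 1.2816)² × 1² / 1² = 17.1, so 18 per arm and 36 in total, not 68.
- 34 per arm would need SD = √(34 / 17.13) = 1.41.
- Superiority, SD 1: 2 × (1.96 + 1.2816)² = 21.0, so 22 per arm, not 39.
- 39 per arm would need SD = √(39 / 21.02) = 1.36.

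The stated numbers do not follow from SD 1. They imply an unstated SD of roughly 1.4, so both values are carried forward.

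**Step 2: variance, adjusted against the level.** The ratio is 1 - r².
- r = 0.3: 0.91, a cut of 9%; 78 women then give the precision of 78 / 0.91 = 86.
- r = 0.5: 0.75, a cut of 25%; 78 / 0.75 = 104.

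**Step 3: variance, adjusted against change from entry**, with outcome SD 1.
- Screening SD 0.7: variance of change = 1 + 0.49 - 1.4r, which is 1.07 at r = 0.3 and 0.79 at r = 0.5. Ratios are 0.91 / 1.07 = 0.85 and 0.75 / 0.79 = 0.95, cuts of 15% and 5%.
- Equal SDs: variance of change = 2(1 - r), which is 1.40 and 1.00. Ratios are 0.65 and 0.75, cuts of 35% and 25%.

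**Step 4: interval and power for the level, 39 per arm** (normal approximation). SE = SD × √(2/39) × √(1 - r²), with r = 0 for the unadjusted test. Half-width of the 90% interval = 1.645 × SE. Non-inferiority power = Φ((1 + d)/SE - 1.645) at true difference d. Superiority power = Φ(d/SE - 1.96).

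| | Unadjusted | r = 0.3 | r = 0.5 |
|---|---|---|---|
| Half-width, SD 1 (g/dL) | 0.37 | 0.36 | 0.32 |
| Half-width, SD 1.4 (g/dL) | 0.52 | 0.50 | 0.45 |
| Non-inferiority power, SD 1, d = 0 | 99.7% | 99.9% | >99.9% |
| Non-inferiority power, SD 1.4, d = 0 | 93% | 95% | 98% |
| Non-inferiority power, SD 1.4, d = -0.3 | 71% | 75% | 82% |
| Superiority power, SD 1.4, d = 1 | 88% | 91% | 95% |
| Superiority power, SD 1, d = 0.5 | 60% | 64% | 72% |

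The true differences of -0.3 and 0.5 are assumptions; 1 g/dL is the plan's superiority effect. The formulas ignore the two degrees of freedom spent on the covariates, which is little with 78 women. If r were near 0 there would be no gain.

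**Step 5: validity.** In 20,000 simulated trials at the -1 limit (39 per arm, SD 1, r = 0.5, an assumed trimester effect of 0.4 g/dL, trimesters mixed 50:50), the one-sided error rate was 4.9% for the unadjusted level, 4.9% for change and 4.8% for the adjusted model. Adjustment does not repair an error rate, because none is broken.

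**The case against.** The strongest reply is that an unadjusted t test in a randomized trial is legitimate, and that at the plan's stated SD the choice hardly affects the verdict: non-inferiority power at no true difference is 99.7% before any adjustment. That stands. The larger gains in the table need an SD near 1.4, a true deficit, or a benefit smaller than 1 g/dL. The correlation is also unknown, and because eligibility caps screening hemoglobin from above, it may be low.

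Three stronger readings are tempting, and the documents do not support them.

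- *Screening hemoglobin is ignored under either outcome.* This is not so for change from entry, which subtracts it, though with weight 1 rather than the weight that the data would choose.
- *Hemodilution makes entry trimester a large source of error.* The Background says "Total blood volume increases by approximately 50% and red blood cell mass increases by 25" per cent. Those figures describe a whole pregnancy without timing, while these women are already pregnant at screening. Dilution still to come would affect mainly change from entry; the third-trimester level is measured late in pregnancy whenever the woman entered. The only trimester contrast in the plan is the 0.5 g/dL between the cut-offs. An effect of that size, mixed 50:50, adds variance 0.25 × 0.5² = 0.0625, about 6% at SD 1. Removing it takes the half-width only from 0.37 to 0.36 g/dL.
- *Chance imbalance biases the non-inferiority test.* Imbalance can shift the estimate in the trial that is actually run, but under randomization the unadjusted standard error already allows for it. It is the same loss of precision, not a second harm.

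**Conclusion.** The point holds as a matter of efficiency. The primary comparison is valid but uses screening hemoglobin either not at all (level) or with a fixed weight (change), and entry trimester in neither case. For an assumed r of 0.3 to 0.5, adjustment removes 9% to 25% of the variance of the level. Against change from entry it removes 5% to 15% if the screening SD is 0.7, or 25% to 35% if the two SDs are equal.

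The benefit is a narrower interval around the treatment difference. Power also rises for superiority, and for non-inferiority if the true SD is nearer the roughly 1.4 implied by the stated 68. Nothing here corrects type I error, and the documents do not show that the non-inferiority conclusion would change. Label: free improvement.

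**What to change.** In section 14, make the primary analysis a linear regression of third-trimester hemoglobin on arm, screening hemoglobin, and gestational age (or trimester) at screening. Compare the lower confidence limit of the adjusted mean difference with -1 g/dL, and report the unadjusted difference as a sensitivity result.

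This brings two further benefits. With screening hemoglobin in the model, the estimated treatment difference is the same whether the outcome is the level or change from that screening value, so the choice between the two no longer affects the estimate. The model also supplies a mean difference with a confidence limit to set against -1, which a rank-sum test does not. Naming the covariates now prevents their being chosen after the data are seen, in a trial that is open label.

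Cost: one sentence in section 14 and one Stata command. Screening hemoglobin and trimester are already needed for eligibility, so no new samples, visits or patients are required. Gestational age in weeks is presumably in the prenatal chart; if not, trimester serves.
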